### **1.2. Study Design**

This is a randomized, double-blind, placebo-controlled, multinational, multicenter Phase 3 study to determine if subjects with mHSPC will benefit from the addition of apalutamide to ADT. Enrollment of approximately 1,000 subjects is planned for this study. Subjects who meet all of the inclusion criteria and none of the exclusion criteria will be stratified by Gleason score at diagnosis, prior docetaxel use, and geographic region, and then randomly assigned in a 1:1 ratio to the apalutamide plus ADT or matching placebo plus ADT group.

The study will include a Screening Phase of up to 28 days before randomization to establish study eligibility. Subjects will receive treatment in 28-day treatment cycles during the Treatment Phase until

disease progression or the occurrence of unacceptable treatment-related toxicity. Subjects must discontinue study drug with documented clinical progression. After discontinuation of study drug, subjects will have an End-of-Treatment Visit within 30 days after the last dose of study drug. In the event of a positive study result at either of the interim analyses or at the final analysis, all subjects in the Treatment Phase will have the opportunity to enroll in an Open-label Extension Phase, which will allow subjects to receive active drug (apalutamide) for up to 3 years.

Subjects will be monitored for safety starting from the signing of informed consent until 30 days after the last dose of study drug. Adverse events including laboratory AEs will be graded and summarized using the National Cancer Institute Common Terminology Criteria for Adverse Events (NCI-CTCAE) Version 4.03. Dose modifications will be made as required according to dose modification rules. An Independent Data Monitoring Committee (IDMC) will be commissioned for the study to provide recommendation during the planned interim efficacy analysis and regular safety review.

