## **5.1. Analysis Specifications**

### **5.1.1. Level of Significance**

In general, a two-sided significance level of  $\alpha = 0.05$  will be used for all hypothesis testing and all CIs will be calculated on the two-sided 95% confidence level, unless otherwise specified.

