### **3. EXPOSURE ADJUSTED INCIDENCE RATES (EAIR)**

#### **3.1. Restriction on the first event**

The analysis restricts on the occurrence of the first event per patient and ignores the existence of later (multiple) events as these cannot be assumed to occur independent of previous events (e.g.: patients suffering from infections may have in general a higher risk of having other complications and may even have a higher risk of getting other infections). The occurrence of multiple events is subject to another analysis considering the absolute number of adverse events per patient.

For these reasons the EAIR should be interpreted as 'rate until the first event occurs'. Rates estimated from several patients can be averaged on the level of a preferred term (PT), of a system organ class (SOC), or on a global level (see below).

The interpretation of EAIRs is simple and consistent on the preferred-term level only, and can be expressed as "Average number of TEAEs per preferred-term emerging per person-month of exposure".

The aforementioned considerations apply in the same way to EAIRs estimated on the global level: when EAIRs are collapsed into the global estimate (first analyses), the estimate can be interpreted as the "Average number of TEAEs emerging per person-month and PT", because estimation has been performed on a 'per PT'-basis (per average or typical PT among all PTs). Comparing EAIRs on the level of the SOC or on the global level involves data destruction because a patient's information is reduced to the first TEAE only (and possibly to a TEAE of marginal relevance among many TEAEs with higher clinical relevance).

The EAIR analysis focuses on the 'speed' by which TEAEs emerge. The analysis restricts on the first event of a patient because independence of TEAEs cannot be assumed. The necessity to restrict on the first event entails considerable data destruction when deriving SOC-specific EAIRs or the EAIR on a global level. To overcome this, the 'per PT'-analysis, which is reported in both Tables identically, is preferable.

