Comparing EAIRs between the analyses outlined below on a SOC-specific or a global level demonstrates that the 'per PT'- method makes the interpretation of results more difficult. However, it can be suggested that this method provides a more robust approach when the two treatment arms are to be compared on a SOC-specific or global level. A t-Test like comparison of PT-specific estimates between the two treatment arms may provide a more robust, comprehensive and easy-to-communicate way of visualizing and comparing results.

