### 3.2. Duration of exposure: censored & non-censored

The incidence rate for a patient is derived from the duration of exposure to treatment of that patient. When averaging incidence rates a patient's duration of exposure is given either A) by the time when the event has occurred (non-censored data), or B) by the total duration of treatment in case the patient does not show the adverse event in question (censored data). Depending on whether a patient has an adverse event or not, the duration of exposure enters the denominator in its non-censored or censored form, respectively.

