### 3.5. EAIRs on the level of a SOC and on the global level on a ‘per-PT’ basis

#### 3.5.1. Average EAIR per PT

The EAIR for a specific PT is an average over all patients, i. e.

$$EAIR_{PT} = \frac{\sum TEAE_{PT,i}}{\sum t_{PT,i}}, \quad i=1, \dots, n_{PT}$$

whereby the number of TEAEs and durations of exposure enter the nominator and the denominator.

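### The t-test over preferred-term rates suggested in SAP Attachment 1 would, if preferred terms are its observations, use the wrong unit and miss its nominal error rate in either form

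*SAP*

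**What the plan says.** Attachment 1 of the SAP adds exploratory analyses for health-economic and reimbursement use, among them exposure-adjusted incidence rates (EAIRs). For each preferred term, section 3.5.1 divides first events by summed exposure: "The EAIR for a specific PT is an average over all patients". Under section 3.2, exposure runs to the event, or is given "by the total duration of treatment in case the patient does not show the adverse event in question".

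Section 3.1 then discusses how to compare the arms at system organ class (SOC) or global level. It calls the per-PT method the more robust one for that purpose and adds that "A t-Test like comparison of PT-specific estimates between the two treatment arms may provide a more robust, comprehensive and easy-to-communicate way" to display and compare the results. It does not say whether PTs are paired across arms, whether rates or log rates are used, what the error term is, or at what level the test is made. The only level available is the general 0.05 default in SAP section 5.1.1, which "will be used for all hypothesis testing and all CIs will be calculated on the two-sided 95% confidence level".

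The same section gives the reason for keeping only first events: "The analysis restricts on the first event of a patient because independence of TEAEs cannot be assumed". Its example is that "patients suffering from infections may have in general a higher risk of having other complications".

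**The concern.** A t-test over PT estimates takes the PT as its observation and the spread across PTs as its error. The randomised unit is the patient. Each patient contributes to every PT rate in his arm, so a group of event-prone patients raises many PT rates together. Keeping first events removes repeats within a PT but leaves this correlation between PTs, which is the kind the SAP's own example describes.

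The two usual forms of the test go wrong in opposite directions. An unpaired test counts the gap between common and rare PTs, which is shared by both arms, as sampling error, so it hardly ever rejects. A paired test removes that gap but ignores the correlation, so its standard error is too small. A reimbursement dossier could then show a spurious difference in adverse event burden or miss a real one, depending on a choice that the SAP leaves open.

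**Working it through.** The SAP states no error rate, power or sample size for this comparison, so there is no figure to reproduce.

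**Inputs from the documents.** About 1,000 subjects (SAP section 1.2: "Enrollment of approximately 1,000 subjects is planned for this study"), 1:1, hence 500 per arm; EAIR per PT equal to first events over summed exposure; two-sided 0.05 by default.

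**Assumed inputs, not in the documents.** 50 or 200 PTs; m distinct PTs per patient (simulation targets 3 and 6); gamma patient frailty with mean 1 and variance v = 0, 0.25, 0.5 or 1.0, shared across PTs; log-normal PT rates with log-SD 1.2 (0.6 as a check); treatment time exponential with mean 30 months, capped at 30.

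**Formula for the paired test.** With frailty, a patient's total over PTs has mean m and variance about m + v·m². A test that takes PTs as independent allows for about m. The ratio of true to assumed variance is therefore about 1 + v·m, and the type I error is 2·[1 − Φ(1.96/√(1 + v·m))].

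Example: v = 0.5 and m = 6 give 1 + 3 = 4, √4 = 2, 1.96/2 = 0.98, and an error rate of 33%.

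| m | v = 0 | v = 0.25 | v = 0.5 | v = 1.0 |
|---|---|---|---|---|
| 2 | 5% | 11% | 17% | 26% |
| 6 | 5% | 22% | 33% | 46% |
| 10 | 5% | 30% | 42% | 56% |

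An error rate of 60% needs v·m of about 13: √14 = 3.74, 1.96/3.74 = 0.524, giving 60%.

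**Simulation under the null.** 600 replicates per row; the Monte Carlo standard error is about 0.9 points at 5% and 1.9 points at 35%. Entries are the percentage rejecting at nominal 5%.

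| v | PTs (events per patient) | Unpaired, rate | Paired, rate | Unpaired, log | Paired, log | Patient as unit |
|---|---|---|---|---|---|---|
| 0 | 50 (2.69) | 0.0 | 3.2 | 0.0 | 4.0 | 4.0 |
| 0 | 200 (5.63) | 0.0 | 5.7 | 0.0 | 5.0 | 5.5 |
| 0.25 | 50 (2.63) | 0.0 | 13.3 | 0.0 | 7.5 | 5.7 |
| 0.25 | 200 (5.54) | 0.0 | 23.8 | 0.0 | 12.5 | 4.8 |
| 0.5 | 50 (2.58) | 0.0 | 21.3 | 0.0 | 11.5 | 5.5 |
| 0.5 | 200 (5.48) | 0.0 | 34.3 | 0.0 | 19.7 | 4.7 |
| 1.0 | 50 (2.50) | 0.0 | 31.0 | 0.0 | 16.5 | 6.2 |
| 1.0 | 200 (5.35) | 0.0 | 43.8 | 0.3 | 26.5 | 5.8 |
| 0.5, log-SD 0.6 | 200 (5.76) | 1.0 | 36.3 | 2.3 | 30.0 | 3.3 |

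The formula agrees: v = 0.5 and m = 5.48 give 1 + 2.74 = 3.74, √3.74 = 1.93, 1.96/1.93 = 1.01, or 31%, against 34.3% simulated. Further simulations under other assumed inputs gave 11% to 59% for the paired test on the rate scale and up to 43% on the log scale.

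**Power (200 PTs, v = 0.5).** At a true rate ratio of 1.25, the unpaired test rejected in 5.8% of trials on the rate scale and 41.2% on the log scale. The same mean-over-PT difference, with its variance taken from patients, rejected in 96.7%. Other set-ups put the unpaired rate-scale figure at up to about 11%. At a ratio of 1.5 the unpaired rate-scale test reached 95%, so the loss matters for moderate differences.

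**The case against.** The sentence is tentative, mentions display as well as comparison, and belongs to an attachment labelled exploratory. It defines no statistic, pairing, scale or decision rule, and no table depends on it. An error rate can therefore be given only to a completed version of the procedure, not to what is written. This stands.

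The words could also mean one comparison per PT, each with a standard error from patients. The patient would then be the unit, and the issue would be multiplicity. The text does not exclude this, but the sentence just before speaks of comparing arms at SOC or global level, which favours PTs as observations. That PTs would be treated as independent is inferred from the form of the test; no adjustment is described.

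The claim of robustness is made relative to SOC and global rates that reduce a patient to his first event. That is a fair complaint about lost information, but it does not give a t-test over PTs valid error bars.

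A reader might infer that the plan commits to a test with a false-positive rate of half or more. The documents do not support that. By the formula, 48% at v = 0.5 needs about 13 distinct PTs per patient, a figure they do not contain. The mildest correlated case simulated gave 7.5%.

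**Conclusion.** The point holds conditionally, as a minor one. If PTs are the observations, neither usual form of the test is sound. Unpaired, it rejects in about 0–2% of null trials, even without correlation, and has about 6–11% power on the rate scale at a true ratio of 1.25. Paired, it exceeds its level, at roughly 8–60% depending on scale, number of PTs, events per patient and frailty variance. The paired figures should be read as a range, because these inputs are assumed. The direction is firmer: among the cases simulated, the paired test was near 5% only with independent PTs, which section 3.1 says cannot be assumed.

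A reader might go further and infer that the trial's safety findings are unreliable. They are not touched: the main adverse event analysis in SAP section 6.1 is a summary by arm, and no primary or secondary analysis uses EAIRs.

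**What to change.** Delete the t-test sentence from Attachment 1, section 3.1. Then do one of the following:

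- Show PT-level EAIRs by arm descriptively, with no test across PTs.
- Compare arms on the per-PT summary, or on the SOC and global rates already defined in sections 3.6.2 and 3.6.3, with a confidence interval from a bootstrap of patients or a permutation of treatment labels within the randomisation strata (Gleason score, region, prior docetaxel).

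The per-PT summary keeps the information that section 3.1 wants to preserve; the rates in 3.6.2 and 3.6.3 are simpler to interpret but use only each patient's first event. In the simulations above, taking the variance from patients held the error rate at 3.3–6.2%; a patient bootstrap or permutation applies the same principle. The cost is a wording change and a short program, with no new data.

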### 3.2. Duration of exposure: censored & non-censored

The incidence rate for a patient is derived from the duration of exposure to treatment of that patient. When averaging incidence rates a patient's duration of exposure is given either A) by the time when the event has occurred (non-censored data), or B) by the total duration of treatment in case the patient does not show the adverse event in question (censored data). Depending on whether a patient has an adverse event or not, the duration of exposure enters the denominator in its non-censored or censored form, respectively.

### 3.3. Incidence rate per patient

The incidence rate for a specific event of a patient  $i$  is the reciprocal of time  $t$  when the first event occurs:

$$EAIR_i = 1/t_i$$

### 3.5. EAIRs on the level of a SOC and on the global level on a ‘per-PT’ basis

#### 3.5.1. Average EAIR per PT

The EAIR for a specific PT is an average over all patients, i. e.

$$EAIR_{PT} = \frac{\sum TEAE_{PT,i}}{\sum t_{PT,i}}, \quad i=1, \dots, n_{PT}$$

whereby the number of TEAEs and durations of exposure enter the nominator and the denominator.

#### 3.5.2. Average EAIR per SOC

The average EAIR per SOC considers the first event of each patient within the SOC. The denominator includes the exposure time of each adverse event of all PTs within the SOC, per patient, i. e.

$$EAIR_{SOC} = \frac{\sum TEAE_{SOC,i}}{\sum t_{PT,i}}, \quad \text{in } PTs \text{ per } SOC, \quad PT=1, \dots, n_{PT}$$

where  $TEAE_{SOC,i}$  is the first event per patient per SOC and  $t_{PT,i}$  is the exposure time for a specific preferred term of a given patient.

Note: This EAIR is an incidence rate per average (or typical) preferred term in that SOC (cf. 3.6.1).

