#### 3.5.3. Average EAIR on a global level

The average EAIR on a global level only considers the first event per patient across all events.

The denominator includes the exposure times of all PTs, i. e.

$$EAIR_{global} = \frac{\sum TEAE_i}{\sum t_{PT,i}}, \quad \text{in } PTs, \quad PT=1, \dots, n_{PT}$$

where  $TEAE_i$  is the first event of a patient overall and the  $t_{PT,i}$ 's are PT-specific exposure times of that patient.

Note: This EAIR is an incidence rate per average (or typical) preferred term.

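### SAP Attachment 1, 3.5.2 and 3.5.3: one first event per patient over exposure summed across all preferred terms is not the per-term rate it is labelled, and it falls as exposure lengthens

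*SAP*

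**What the plan says.** SAP Attachment 1 sets out two sets of EAIRs.

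In the first set, at SOC level (3.5.2), the numerator is limited: "The average EAIR per SOC considers the first event of each patient within the SOC". The denominator is not: "The denominator includes the exposure time of each adverse event of all PTs within the SOC, per patient". The note states what the figure is meant to be: "This EAIR is an incidence rate per average (or typical) preferred term in that SOC". Section 3.5.3 does the same over all events: "The average EAIR on a global level only considers the first event per patient across all events", while "The denominator includes the exposure times of all PTs". Section 3.1 of the attachment reads the global figure as "Average number of TEAEs emerging per person-month and PT". Under section 3.2, a patient without the event in question contributes the whole treatment duration.

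In the second set (3.6.2 and 3.6.3), the same first event is divided by a single exposure time per patient. Those sections remark that the earlier denominator depends on how many PTs there are.

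The PT-level rate is the same in both sets (3.5.1 and 3.6.1). On the choice between methods at SOC or global level, section 3.1 first concedes that the per-PT method is harder to interpret, then says "it can be suggested that this method provides a more robust approach when the two treatment arms are to be compared" at those levels.

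**The concern.** A rate per typical PT needs the first event of each PT in the numerator, because each PT contributes its own exposure time to the denominator. In 3.5.2 and 3.5.3 a patient can add only one event but adds one exposure time for every PT. The note to 3.5.2 refers to 3.6.1, whose numerator does count PT-specific first events, yet 3.5.2 does not use that numerator.

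The mismatch does more than rescale the figure. Once a patient has had a first event, later first events in other PTs are not counted, while exposure for the remaining PTs keeps accruing. The longer the treatment, the more uncounted time enters. If the arms differ in treatment duration, a comparison meant to adjust for exposure would itself depend on exposure, in favour of the arm treated longer.

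**Working it through.** The SAP gives no numerical EAIR, so there is no figure to reproduce. I evaluated its formulas directly.

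**Inputs.** The numerators and denominators are those of Attachment 1, 3.5.2, 3.5.3, 3.6.2 and 3.6.3, with the section 3.2 rule for patients without the event. The exposure medians of 20 and 30 months are the planning rPFS medians (SAP section 1.4), used as a proxy because treatment runs to progression (SAP section 1.2; Protocol section 9.1.3). The documents give neither the number of PTs, K, nor the monthly hazard per PT, λ. I assumed K = 5, 20 and 200, and λ = 0.0005, 0.002 and 0.01, with independent constant hazards.

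**Closed form, exponential exposure with rate μ.** The chance of any first event on treatment is Kλ/(Kλ+μ). The mean summed exposure is K/(λ+μ). So the 3.5.2/3.5.3 figure is

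λ(λ+μ)/(Kλ+μ).

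It equals λ only when K = 1. For K ≥ 2 it falls as mean exposure 1/μ rises.

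**Equal true rates.** μ = ln 2/20 = 0.03466 (control) and ln 2/30 = 0.02310 (apalutamide). For K = 20, λ = 0.002:

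- control: (0.002 + 0.03466)/(0.04 + 0.03466) = 0.491 of the true PT rate
- apalutamide: (0.002 + 0.02310)/(0.04 + 0.02310) = 0.398
- apparent ratio: 0.398/0.491 = 0.81, against a true 1.00

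| K | λ per month | Formula ÷ true PT rate, control | Same, apalutamide | Apparent ratio |
|---|---|---|---|---|
| 5 | 0.0005 | 0.946 | 0.922 | 0.97 |
| 5 | 0.002 | 0.821 | 0.758 | 0.92 |
| 5 | 0.01 | 0.528 | 0.453 | 0.86 |
| 20 | 0.0005 | 0.787 | 0.713 | 0.91 |
| 20 | 0.002 | 0.491 | 0.398 | 0.81 |
| 20 | 0.01 | 0.190 | 0.148 | 0.78 |
| 200 | 0.0005 | 0.261 | 0.192 | 0.73 |
| 200 | 0.002 | 0.084 | 0.059 | 0.70 |
| 200 | 0.01 | 0.022 | 0.016 | 0.75 |

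With fixed exposure of 20 and 30 months, the ratio runs from 0.99 to 0.67 over the same grid.

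**Not the SOC rate either.** At K = 20, λ = 0.002, the SOC rate is 20 × 0.002 = 0.040 per month. Section 3.5.2 returns 0.002 × 0.491 = 0.0010 (control) and 0.002 × 0.398 = 0.0008 (apalutamide).

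**Pull towards 1 at equal exposure.** With fixed exposure T the figure is λ(1−e^(−KλT))/[K(1−e^(−λT))]. Take K = 10, T = 20 and a true ratio of 1.5 (λ = 0.005 and 0.0075). The figures are 0.0005 × 0.632/0.0952 = 0.00332 and 0.00075 × 0.777/0.1393 = 0.00418, a ratio of 1.26.

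**Reversal.** With medians of 20 and 30 months and hazards truly 20% higher in the longer-exposed arm (λ = 0.0024 against 0.002), K = 20 gives 0.0024 × 0.02550/0.07110 = 0.00086 against 0.00098, a ratio of 0.88. At K = 200 it is 0.72.

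**The alternatives.** The 3.6.2 form gives [Kλ/(Kλ+μ)]/[1/(Kλ+μ)] = Kλ, whatever μ is, so equal rates return 1.00. A simulation (40,000 patients per arm, exponential exposure) gave 0.99–1.01. Counting every PT's first event over the summed PT exposure returns λ when PT rates are equal. With strongly unequal rates (0.03, 0.01, 0.005 and seventeen PTs at 0.0005), that pooled version still gave 0.91. The mean of the PT-specific EAIRs does not drift under constant hazards, because each PT's EAIR estimates its own hazard.

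**The case against.** **A different reading of the denominator.** One might hope that only PTs the patient actually experienced are summed. Section 3.2 and the contrast drawn in 3.6.2 and 3.6.3 rule this out.

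**The SAP does not prefer these formulas.** A reader might infer that the defective version is the SAP's chosen analysis. The text does not support that. What section 3.1 of the attachment calls preferable is the analysis reported identically in both tables, which is the PT-level EAIR of 3.5.1 and 3.6.1, and that is sound. Its remark about robustness at SOC and global level is tentative, follows an admission of harder interpretation, and leads on to a comparison of PT-specific estimates. This stands. The remark still points the reader to the wrong figure for those two levels.

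**Limited reach.** The attachment is exploratory and serves health economics and reimbursement. It already contains a coherent SOC and global rate, and warns that interpretation is straightforward at PT level only. The safety tables of SAP section 6.1 use counts and percentages and no EAIR. This stands too, so an inference that the trial's main safety conclusions are biased would be unfounded.

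**Assumed size.** PT counts, hazards and exposure are not in the documents, and with few PTs and rare events the distortion is negligible (0.97–0.99 at K = 5, λ = 0.0005). A reader might also infer that the plan states longer exposure on apalutamide. It does not: treatment may continue past radiographic progression (Protocol sections 9.1.3 and 10.2) and may stop for toxicity. What follows from the formula is only that it favours whichever arm is exposed longer.

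**The alternative is not perfect.** When patients differ in susceptibility (gamma frailty with variance 1), the 3.6 rate also drifts, to 0.90–0.95, but the 3.5 rate in the same runs gave 0.72–0.90.

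**Conclusion.** Sections 3.5.2 and 3.5.3 are wrong as written. The notes claim one quantity, the rate for a typical PT. The figure is not that, and it is not the SOC or global rate of 3.6.2/3.6.3.

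For K ≥ 2 and constant hazards, the dependence on exposure is a property of the formula. Its size is conditional. With exposure medians of 20 and 30 months, equal true rates show as anything from 0.97 (few, rare PTs) to about 0.70 (global level), and a true excess of 20% in the longer-exposed arm can appear as a deficit. That apalutamide would be this arm is an inference from the planning medians.

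Severity is minor, since the affected figures are two summaries in an exploratory attachment.

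**What to change.** - Delete 3.5.2 and 3.5.3 of Attachment 1, and use 3.6.2 and 3.6.3 for SOC and global comparisons.
- If a per-PT summary is wanted at those levels, report the mean of the PT-specific EAIRs. Replacing only the numerator with all PT first events is not enough when PT rates differ strongly.
- Remove the closing suggestion in Attachment 1 section 3.1 that the per-PT method is more robust for comparing arms at SOC or global level. Also remove the reading of the global figure as a per-PT rate.

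The cost is a wording change to an attachment and minor programming. No data collection or main analysis changes.
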